PCT1101.003	October 31, 2012	The protocol has been revised to address the concerns posed by FDA in their disapproval letter to CryoLife, Inc. dated 02 May 2012 and in the e-mail correspondence dated 08 May 2012. Other changes that are outside the scope of the concerns posed by FDA include: 
 • Removal of blood count and coagulation status as a safety endpoint (Sections 1, 6.1.3, and 6.6.4); • Device description; • Increase of the maximum investigational sites to 12 (Sections 1 and 6.3; sample Subject Informed Consent Form); • Change in the manufacturer of the Investigational Product to CryoLife, Inc. (Section 2.2); • Clarification that PerClot results in a less severe foreign body response/inflammatory reaction when compared to gelatin sponge and bone wax (Section 3); • Clarification that specific sites will be evaluated for satisfaction of intraoperative eligibility criteria (Section 6.4.3); and • Update of company logo in the Instructions for Use.
PCT1101.004	May 10, 2013	The protocol has been revised to address the concerns posed by FDA in their disapproval letter to CryoLife, Inc. dated 14 December 2012. Other changes that are outside the scope of the concerns posed by FDA include: 
 • Removal of the 3 minute hemostatic assessment time point (Sections 1, 5.1, 6.1.3, 6.2.3, 6.4.3.5, 6.6.3; 6.6.11; Sample Case Report Forms); • Increase of the maximum investigation sites to 15 (Sections 1 and 6.3, sample Subject Informed

Protocol Number	Effective Date	Detail of Changes
		
Consent Form);
 
 • Addition of contraindication for use in patients who have known sensitivity to starch or starch-derived materials (Section 6.3.2, PerClot Instructions for Use, Sample Subject Informed Consent Form, Sample Screening and Enrollment Log, Sample Case Report Forms); • Addition of information regarding the comparator device (Section 6.2.2); • Revision of the Risk Analysis in accordance with ISO14971:2012; and • Revision of the sample Principal Investigator and Sub-Investigator Agreements to use consistent legal terms, reference the Clinical Research Agreement, and include language on the Physician Payment Sunshine Act.
PCT1101.005	September 26, 2013	
The protocol has been revised to address the concerns posed by FDA in their conditional approval letter to CryoLife, Inc. dated 14 June 2013 and telephone communication on 12 July 2013. Other changes that are outside the scope of the concerns posed by FDA include:
 
 • Statement regarding destruction of opened investigational product (Section 2.3) • Additional biocompatibility testing (Section 3.1) • Addition of ROM, DVT, and Hemoglobin assessments for subjects undergoing orthopedic procedures (Sections 4.2, 6.4.2, 6.4.4, 6.4.5, Appendix B, Appendix E, Appendix F) • Appendix G has been revised as in vivo training is no longer necessary due to the removal of the bleeding severity assessment model.
PCT1101.006	February 18, 2014	
The protocol has been revised to address the concerns posed by FDA in their conditional approval letter to CryoLife, Inc. dated 30 October 2013 and telephone communication 17 January 2014. Other changes that are outside the scope of the concerns posed by FDA include:
 
 • Addition of Biocompatibility PreClinical Studies • Addition Thromboembolism Assessment • Addition Appendix L: Blood Sugar Lowering Medications • Appendix O: Operative Steps
PCT1101.007	March 31, 2014	Corrections to protocol per G11007s2a1 interactive review questions with the FDA dated 24 March 2014.

Protocol Number	Effective Date	Detail of Changes
PCT1101.008	April 15, 2014 July 28, 2014	
Formatting throughout document. Changes per FDA Approval Letter dated March 27, 2014 study design considerations.
 
The following changes have been made:
 
 Primary and secondary endpoints have been revised to 7 minutes and 5 minutes, respectively. Hemostasis defined. Maximum dose increased to 10 grams. Revisions to IFU and Operative Steps regarding product administration. Compliance Statement change. Revisions to assessment method for pulmonary embolism. Allocation eCRF removed. Protocol Deviation eCRF created. List of Principal Investigators revised. Statement regarding masking added to Sections 1, 2, and 6.1.2. Statement regarding subject numbering added to Section 6.4.1. Section 3.2.19 added (preclinical study). Revision of 25-minute intraoperative hemostatic evaluation to 35-minute intraoperative hemostatic evaluation in Section 4.2. Intraoperative inclusion for bleeding flux revised. Statement regarding dislodgement of study device added to Section 6.4.3.4. Standard gauze revised to Covidien™ Vistec™ X-ray Detectable sponges. Study duration modification. Removal of legally authorized representative throughout protocol, ICF, and applicable CRF page. Appendix C revised to reflect changes to IFU. Appendices rearranged. Clarifying language throughout document.
PCT1101.009	December 1, 2014	
Changes per FDA Approval Letter dated August 29, 2014 study design considerations and Q-Sub Call on November 11, 2014.
 
The following changes have been made:
 
 Removal of language regarding multiple bleeding sites throughout protocol, Informed Consent Form, and Case Report Forms. Hemostasis maintenance assessment for an additional 5 minutes(12 minutes post-application) added to protocol, Informed Consent Form, and Case Report Forms Addition of intraoperative inclusion criteria related to

Protocol Number	Effective Date	Detail of Changes
		
size of study device application area to Sections 6.3.2, 6.4.3.2, and Appendix D.
 
 • Bleeding flux inclusion criteria revised in Sections 6.3.2 and 6.4.3.2. • Information regarding responsibilities of randomization designee added to Section 6.4.3.3. • Information regarding calibration of scales added to Section 6.4.3.2. • Bleeding severity score added to randomization stratification in Section 6.6.6. • Additions to Glossary. • Revisions to Appendix A. • Appendix C revised to reflect changes to IFU. • Calibration eCRF created. • Revisions to Appendix N. • Addition of clinical investigation sites on page xii. Grammatical corrections, consistent terminology, and clarifying language added throughout document.
PCT1101.010	January 7, 2015	
Changes per FDA teleconference on December 23, 2014.
 
The following changes have been made:
 
 • DVT prophylaxis methods and duration added to Sections 6.4.5 and 6.4.6. • Case Report Forms 5 and 6 revised to include DVT prophylaxis methods and duration. • Revisions to Appendix N: the wording “and multiply those two values” was added and the type of “Anatomic Site” and “Anatomic Application Site” was changed to bold.
PCT1101.011	February 17, 2015	
 • Removal and addition of clinical investigation sites on page xii. • Reference to envelope-based randomization methods removed in Section 6.4.3.3 and Appendix N. • Insertion of Interactive Web Response System (IWRS) in Section 6.4.3.3 and Appendix N. • Clarifying language added regarding subject numbering in Section 6.4.1. • Version number and copyright date revised in Appendix A. • Correction of typos and grammatical errors throughout the document.
PCT1101.011 (02/15) Amendment 1	April 27, 2016	
 • Investigator Training (Appendix G) has been removed and replaced with the Protocol Signature Page. • Principal Investigators & Investigational Sites removed. • Sections 1, 6.3, 6.4.6, 6.4.7 Table 3, and Appendix B

Protocol Number	Effective Date	Detail of Changes
		
have been revised to reflect a follow up period of 6 weeks.
 
 • Unscheduled visit added to Section 6.4.6, Laboratory and Follow up Case Report Forms. • Sections 6.3.2, 6.4.3.2, and Appendices A and D have been revised to allow inclusion of Class I and II wounds. • A pre-screening log has been added to Appendix D. • Sections 6.4.4 and 6.4.6 have been revised to use consistent language for Thromboembolism Evaluation. • Section 6.4.5 and Discharge Case Report Form revised to remove clinical assessment for signs and symptoms of embolism or thrombosis. • Appendix L revised to include additional blood modifiers. • Appendix N revised to remove reference to Operative Worksheet numbers. • Reference to Case Report Form numbers removed throughout protocol. • Operative Case Report Form modified to facilitate mass calculation of test and control articles. • Figure 1 in Section 6.3 has been revised to show the bleeding severity score. • Appendix J has been revised to include the current version of the inner pouch label. • Section 6.6.5 has been revised to reflect the sample size justification. • Operative Case Report Form has been revised to capture time of application in seconds. • Section 6.3.2, Appendix A, and Appendix D have been revised to remove the word “institution” before “laboratory’s normal reference range.” • Sections 6.3.2 and 6.4.2 have been revised to specify which lab value, if more than one are available, to include in the database. • Window for laboratory evaluation has been revised to 1 month (30 days) in Section 6.3.2. • Section 10.4.2, Table 6 has been revised to remove the requirement for the sites to submit SAE information to the DSMB. • Section 6.4.6.1, Postoperative and Follow up Case Report Forms have been revised to allow an opt-out of CT scan of chest. • Time points for collecting blood glucose have been revised in Section 6.4.4, and Operative, Postoperative, and Laboratory Case Report Forms.

Protocol Number	Effective Date	Detail of Changes
		
 • Clarifying language has been added to Appendix A. • Anticipated enrollment period, maximum duration of clinical investigation, and number of sites has been revised in Sections 1 and 6.3. • Sections 9.1 and 13 have been revised to reflect the current FDA definition of SAE. • Two preoperative exclusion criteria have been changed to intraoperative exclusion criteria in Sections 6.3.2, 6.4.3, and Screening and Operative Case Report Forms. • The preoperative exclusion criterion related to hepatic dysfunction has been replaced with a criterion related to coagulopathy in Section 6.3.2 and Appendices A and D. • Sections 1, 2.3, 6.4.3.3, 6.4.3.4, and Appendix B have been revised to reflect a single-blind study. • Sections 6.3.2, 6.4.4, 6.6.10, Appendices A and B have been revised to remove C3 values as exclusion criteria and add C3 values to the list of covariates and postoperative labs. • Section 6.3.2, and Appendices A and D have been revised to clarify the exclusion criterion regarding GFR and to revise the exclusion criterion regarding glycosylated hemoglobin. • “10g” has been replaced with “the entire contents of up to two 5g bellows” in section 1 and Appendices A, B and N. • Section 6.4.4 has been revised to remove the requirement that any abnormal glucose value be reported as an adverse event. • Sections 6.3.2, 6.4.3.2, and Appendix D have been revised to remove a redundant intraoperative exclusion criterion. • Sections 1, 6.13, 6.6.4, and Appendices A and B have been revised to separate reporting the incidence of procedure complications from incidence of adverse events. • Section 9.3 and Section 10, Table 6 have been revised to clarify adverse event reporting requirements. • Language regarding videotaping and adjudication has been added to Section 6.4.3.5. • Section 6.6.6 has been revised to include the statistical method, change in alpha, and interim analysis. • Appendix B has been revised to include time points for blood glucose measurements, language regarding videotaping, changes to follow up evaluations, and to

Protocol Number	Effective Date	Detail of Changes
		
remove the Principal Investigator signature and date lines.
 
 • Appendix C has been updated. • Storage requirements have been revised in Appendices A and J. • Appendix A has been revised to allow for “up to 70cc of fluid per 1 gram”. • Section 6.3.2 has been revised to allow dermatologic use of corticosteroids. • Section 3.2 was revised to clarify GLP compliance status for two preclinical studies and to remove the study entitled “Preclinical Evaluation Comparing the Efficacy of Two Starch-Based (PerClot vs. Arista) Hemostatic Agents in a Porcine Liver Bleeding Model”. • Additional clinical study summary added to Section 3.3. • Clarifying language throughout protocol.
PCT1101.011 (02/15) Amendment 02	May 25, 2016	
Changes per FDA teleconference on May 24, 2016.
 
 • Sections 6.3.2, 6.4.3, Appendices A, C, D and E have been modified to address FDA’s concerns regarding the use of PerClot in cardiac surgery.
PCT1101.011 (02/15) Amendment 03	June 16, 2016	
Changes per FDA approval letter on May 27, 2016.
 
 • Section 6.4.4, Appendices B and E have been revised to change the time of glucose monitoring. • Section 6.3.2, Appendices A, B, D, and E have been revised to remove the exclusion related to renal dysfunction. • Sections 6.4.3.3, 6.4.3.5, Appendices B and E have been revised to remove acid base status and arterial blood gas testing. • Section 6.4.3 and Appendix A have been revised to include language regarding large needle holes. • Sections 6.3.2, 6.4.3.2, Appendices D and E have been revised to change the wound classification system. • Sections 6.4.4, 6.4.6.1, Appendices B and E have been revised remove the CT scan and Doppler ultrasound. • Sections 1, 6.3, 6.4.6.2, 6.4.7, Appendices B and E have been revised to add a 24 month follow up visit for oncologic subjects. • Section 6.6.6 has been revised to clarify the sample size re-estimation. • Section 6.4.3.3 has been revised to modify the randomization method from IWRS to envelope randomization.

Protocol Number	Effective Date	Detail of Changes
PCT1101.011 (02/15) Amendment 04	July 15, 2016	
Changes per FDA email on July 13, 2016.
 
 Section 4.2 has been revised to note that the CT scan of chest and Doppler Ultrasound will only be performed if clinically indicated. Section 6.6.11 has been revised to include aspirin as a covariate. Appendices E and F have been revised to add a data field regarding aspirin use.
PCT1101.011 (02/15) Amendment 05	November 09, 2016	
 IMARC added as Monitor/Sponsor Representative on cover page and Section 6.5.4. Clarifying language regarding endpoint determination added to Sections 1 and 6.4.3.5. Clarifying language regarding removal/replacement of subjects added to Section 6.6.9. Clarifying language regarding power of the study added to Section 6.6.5. Clarifying language regarding bleeding site added to Section 6.4.3.4. Definition of embolism added to glossary. Clarifying language regarding block randomization process added to Section 6.6.8. Appendices E and F were revised to update the protocol amendment number.
PCT1101.011 (02/15) Amendment 06	February 03, 2017	
 Monitor/Sponsor Representative address updated on cover page and Appendix B. “Urine” removed before “pregnancy test” in Section 4.2, 6.3.2, and Appendices A, B, and D. Note regarding total hysterectomy added to Section 6.3.2. Definition of total hysterectomy added to glossary. Cell saver language clarified in Section 6.4.3.1 and Appendix A. Appendices E and F revised to update the protocol amendment number. Appendix C updated.
PCT1101.011 (02/15) Amendment 07 DRAFT	September 06, 2017	
 Follow up assessments at 24 month visit revised in Sections 1, 6.3, 6.4.6.2, Appendix B, and Appendix E. Definition of overall survival added to glossary.
PCT1101.011 (02/15) Amendment 07	October 24, 2017	
Changes per FDA approval of PCT1101.011 (02/15) Amendment 07 DRAFT
 
 The word “DRAFT” has been removed from protocol number throughout the document. Date of protocol updated.

Protocol Number	Effective Date	Detail of Changes

6.6.13	Missing Data	61
6.7	Data Collection and Data Management	62
6.7.1	Data Retention	62
6.7.2	Study Audits	62
6.8	Protocol Amendments and Deviations.....	63
7	Statement of Compliance	63
8	Informed Consent Process	63
9	Adverse Events	63

9.1	Adverse Event Definitions	63
9.2	Assessing Adverse Events	64
9.3	Reporting Adverse Events	65
9.3.1	UADE Reporting	65
9.3.2	SAE Reporting	65
9.3.3	Subject Death	66
9.4	Data Safety Monitoring Board	66
10	Study Conduct.....	66
10.1	Investigator Selection.....	66
10.2	Investigator Agreements	66
10.3	Confidentiality	67
10.4	Investigator Records and Reports	67
10.4.1	Investigator Records	67
10.4.2	Investigator Reports	67
10.5	Sponsor Records and Reports	69
10.5.1	Sponsor Records	69
10.5.2	Sponsor Reports	69
11	Publication Policy.....	70
12	Bibliography	70
13	Glossary	71
Appendix A: PerClot Instructions for Use		79
Appendix B: Sample Subject Informed Consent Form		85
Appendix C: Risk Analysis		99
Appendix D: Draft Pre-Screening and Screening and Enrollment Log		135
Appendix E: Sample Case Report Forms		140
Appendix F: Operative Worksheet		174
Appendix G: Protocol Signature Page		185
Appendix H: Sample Principal Investigator Agreement		187
Appendix I: Sample Sub-Investigator Agreement.....		193
Appendix J: Labeling		198
Appendix K: Insulin or Blood Sugar Lowering Medications		201
Appendix L: Blood Modifiers		205
Appendix M: NNIS Instructions.....		210
Appendix N: Operative Steps		212
Appendix O: References.....		219

1 Synopsis

The device under investigation is PerClot® Polysaccharide Hemostatic System (hereinafter referred to as PerClot). This is a prospective, multicenter, multidisciplinary, controlled clinical investigation evaluating the safety and efficacy of PerClot compared to a similar marketed hemostatic device.

The overall objective of this clinical investigation is to collect clinical data concerning the safety and efficacy of PerClot versus a similar marketed hemostatic device (the control) in multiple surgical disciplines when used as an adjunct to conventional means of achieving hemostasis such as pressure or ligature. Hemostasis is defined as complete cessation of bleeding.

This will be a single-blinded trial. The subjects will be blinded as to the hemostatic treatment received. Unblinding will be permitted after a subject has completed his or her 6 week follow-up visit evaluation.

The primary objective of this investigation is to demonstrate non-inferiority in the achievement of hemostasis of the treated bleeding site at 7 minutes in subjects receiving PerClot compared to subjects receiving a control hemostatic device. The secondary objective of this investigation is to compare the achievement of hemostasis of the treated bleeding site at 5 minutes in subjects receiving PerClot compared to subjects receiving a control hemostatic device.

The primary endpoint is hemostasis of the treated bleeding site at 7 minutes. The secondary efficacy endpoint for this investigation is hemostasis of the treated bleeding site at 5 minutes. After the 7 minute assessment, the treated bleeding site will be observed for 5 additional minutes (12 minutes post-application) and just prior to closure to assess hemostasis maintenance.

The safety endpoints will consist of:

- Total operative time;
- Hemostasis at 5 and 7 minutes;
- Hemostasis maintenance;
- Total intraoperative estimated blood loss;
- Alternative means required to achieve hemostasis (where applicable);
- Units of blood transfused intraoperatively and postoperatively (where applicable);
- Incidence of reoperation;
- Total hospitalization time;
- The incidence of procedure complications; and
- The incidence of adverse events through final follow-up, including, but not limited to:
 - Adhesions or fibrosis;
 - Anaphylaxis;
 - Blockage of the bladder or ureteral lumen;
 - Blockage of the bypass system;
 - Cancer recurrence and/or progression;
 - Compromised attachment of prosthetic devices to bone or tissue;
 - Death;
 - Embolism;
 - Failure of deep or superficial wound healing;

- Failure to obtain hemostasis;
- Fever;
- Hemorrhage;
- Infection;
- Peri-operative hyperglycemia;
- Exacerbation of surgical procedure-associated adverse events;
- Swelling and compression of pressure-sensitive tissues and structures;
- Thromboembolism;
- Thrombosis; and
- Toxicity.

Three hundred and twenty four subjects across a maximum of 25 investigational sites undergoing open elective cardiac, general, or urological surgical procedures who meet the eligibility criteria will be intraoperatively randomized to receive no more than the entire contents of up to two 5 gram bellows of either the investigational device or a control hemostatic agent on a bleeding site, whose anatomic site is smaller than or equal to 25cm² and whose anatomic application site is smaller than or equal to 47cm², when bleeding is within the pre-defined bleeding severity range after any applicable conventional means for hemostasis are attempted as specified in the intraoperative procedures (Section 6.4.3). Please refer to Section 13 (Glossary) for term definitions. Each investigational site is expected to enroll approximately 13-40 subjects. All investigational sites will be located in the U.S. Follow-up will occur at hospital discharge and 6 weeks post-device application. For oncologic subjects, overall survival data will be collected at 24 months post device application.

2 Investigational Device

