A comparison group of study subjects who are not treated with the investigational agent. The subjects in this group may receive no therapy, a different therapy, or a placebo.

Data

Factual information (such as measurements or statistics) used as a basis for reasoning, discussion, or calculation.

Death

All deaths are considered cardiac unless an unequivocal non-cardiac cause can be established.

Demographic Data

Refers to the characteristics of study participants, including sex, age, family medical history, and other characteristics relevant to the study in which they are enrolled.

Device

An instrument, apparatus, implement, machine, contrivance, implant, in vitro reagent, or other similar or related article, including any component, part or accessory, which is intended for use in the diagnosis, cure, treatment or prevention of disease. A device does not achieve its intended purpose through chemical action in the body and is not dependent upon being metabolized to achieve its purpose.

Device Accountability Records Log

Required documentation for material accountability, quantity used and left over, and date of disposal.

Device Malfunction

A product malfunction or user error, which caused an adverse event.

Dirty

A surgical procedure performed when an active infection is already present.

Discharge Form

A form designed to collect the required protocol information obtained at subject discharge.

Documentation

All forms of records that describe or document study methods, conduct and results, including any adverse events and actions taken.

eCRF

Electronic case report form.

Efficacy

A product's ability to produce beneficial effects on the duration or course of a disease. Efficacy is measured by evaluating the clinical and statistical results of clinical tests.

Embolism

The lodging of an embolus, a blockage-causing piece of material, inside a blood vessel. The embolus may be a blood clot, a fat globule, a bubble of air or other gas, or foreign material.

Enrollment

Enrollment in the study occurs when a patient meets the general inclusion/exclusion criteria, signs the informed consent form, meets the intra operative inclusion criteria and is randomized in the study.

eGFR

Estimated Glomerular Filtration Rate.

Food and Drug Administration (FDA)

Department within the United States Department of Health and Human Services. Enforces Food, Drug and Cosmetics Act and related federal public health laws. Grants IND, IDE, PMA, and NDA approvals.

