
The currently accepted treatment or intervention considered to be effective in the treatment of a specific disease or condition.

Sub-Investigator

Helps conduct investigation at a study site.

Subject

Participant in an investigation. See "Human Subject."

Subject Log

A log designed to document all subjects who undergo a surgical procedure in which bleeding is observed and are enrolled into either the treatment or control arm.

Suture

To unite, close, or secure with a strand of fiber.

Target Application Site

True surface area intended for RSD application in accordance with its Instructions For Use (IFU).

Thrombosis

Local coagulation or clotting of the blood in a part of the circulatory system.

Thromboembolism

Obstruction of a blood vessel by a blood clot that has become dislodged from another site in the circulation.

Total Hysterectomy

Surgical removal of the body, fundus, and cervix of the uterus.

Unanticipated Adverse Device Effect (UADE)

Any serious adverse effect on health or safety or any life-threatening problem or death caused by, or associated with, a device, if that effect, problem, or death was not previously identified in nature, severity, or degree of incidence in the investigational plan or application (including a supplementary plan or application), or any other unanticipated serious problem associated with a device that relates to the rights, safety, or welfare of subjects.

Well-being

Subject's physical and mental soundness.

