	R81	Product administered intravascularly	Thromboembolism Embolism Thrombosis Death	Me	5	Clinical protocol Appropriate use described in IFU Investigator training	PCT1101.011-C (02/15) Amend. 06 L6421	No	Me	5	Yes	N/A
	R82	Product administered into bladder or ureteral lumen	Blockage of the bladder or ureteral lumen	L	4	Clinical protocol Appropriate use described in IFU Investigator training	PCT1101.011-C (02/15) Amend. 06 L6421	No	L	4	Yes	N/A

Risk Analysis

6 of 8

PerClot PHS RM-0011.014

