4.4.4 Safety Analyses

Safety data will be summarized by incidence of each adverse event type along with 95% exact confidence intervals. Adverse event rates will be reported as the proportion of subjects who experience an event and the total number of each event type occurring.

Adverse events will be summarized by relatedness, seriousness, and severity. The comparison of safety between treatment arms will be based on Fisher's exact tests for the proportion of subjects with serious device-related adverse events, unanticipated adverse device effects, and frequent adverse events ($\geq 5\%$ overall incidence) in the two treatment groups.

The other following safety endpoints will also be summarized using descriptive statistics:

- Total operative time;
- Hemostasis at 5 to 7 minutes;
- Hemostasis maintenance;
- Total intraoperative estimated blood loss;
- Alternative means required to achieve hemostasis (where applicable);
- Units of blood transfused intraoperatively and postoperatively (where applicable);
- Incidence of reoperation;
- Total hospitalization time;
- Incidence of procedure complications;
- Incidence of adverse events through final follow-up, including, but not limited to:
 - Adhesions or fibrosis;
 - Anaphylaxis;
 - Blockage of the bladder or ureteral lumen;
 - Blockage of the bypass system;
 - Cancer recurrence and/or progression;
 - Compromised attachment of prosthetic devices to bone or tissue;
 - Death;
 - Embolism;
 - Failure of deep or superficial wound healing;
 - Failure to obtain hemostasis;
 - Fever;
 - Hemorrhage;
 - Infection;
 - Peri-operative hyperglycemia;
 - Exacerbation of surgical procedure-associated adverse events;
 - Swelling and compression of pressure-sensitive tissues and structures;
 - Thromboembolism;
 - Thrombosis; and
 - Toxicity.

Safety analyses are descriptive in nature. There are no formal hypothesis tests associated with these outcomes. All safety analyses will be performed on the ITT population.

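### Embolism, thromboembolism and thrombosis are separate, partly overlapping adverse event types with no combined row, so an excess can stay below the 5% threshold and go untested

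*Protocol*

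**What the plan says.** The Protocol Synopsis, Protocol 6.1.3, Protocol 6.6.4 and SAP 4.4.4 carry the same list. It is introduced by "The incidence of adverse events through final follow-up, including, but not limited to", and Embolism, Thromboembolism and Thrombosis are separate entries.

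Protocol Section 13 (Glossary) defines the terms:

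- Embolism is a blockage-causing piece of material lodged in a vessel: "The embolus may be a blood clot, a fat globule, a bubble of air or other gas, or foreign material".
- Thromboembolism: "Obstruction of a blood vessel by a blood clot that has become dislodged from another site in the circulation".
- Thrombosis: "Local coagulation or clotting of the blood in a part of the circulatory system".

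SAP 4.4.4 makes the type the unit of reporting: "Safety data will be summarized by incidence of each adverse event type along with 95% exact confidence intervals", and "Adverse event rates will be reported as the proportion of subjects who experience an event and the total number of each event type occurring". Fisher's exact tests between arms are planned for serious device-related events, for unanticipated adverse device effects, and for "frequent adverse events ($\geq 5\%$ overall incidence) in the two treatment groups".

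The sponsor's risk analysis (Protocol Appendix C, item R81, intravascular administration) lists the effects of that one hazard as "Thromboembolism Embolism Thrombosis Death". No combined count of these events is planned in either document.

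**The concern.** The definitions overlap where it matters. An embolus may be a clot, and a thromboembolism is an obstruction by a dislodged clot, so a clot embolus satisfies two of the three labels. Neither document says which label takes precedence. The adverse event form (Protocol Appendix E) asks for one CTCAE short name, and nothing links that name to the listed types. The rates in the three rows therefore depend partly on how sites name events, and only the subjects are blinded (Protocol 6.6.8).

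The split also interacts with the testing rule. The comparison of adverse event types applies only to types that reach 5% overall. Related events spread over two or three rows may leave every row below that threshold even when the same subjects, counted together, would exceed it. What is at stake is the between-arm comparison for a hazard that the sponsor's own file rates at its joint-highest residual level.

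**Working it through.** **Denominator.** SAP 4.2.1.1 starts from 154 per arm, and the power stated in SAP Appendix A (0.79885, Farrington-Manning score test) reproduces exactly. The 5% allowance gives 154 × 1.05 = 161.7, rounded to 162 per arm, or 324 in total. Safety is analysed on all randomized subjects, so 162 per arm is used below.

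**Threshold.** 0.05 × 324 = 16.2, so a type needs at least 17 subjects to be tested. At the maximum size, 0.05 × 536 = 26.8, so 27.

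**Test.** For x events on PerClot out of t in total, Fisher's exact test uses P(X = x) = C(162, x) · C(162, t − x) / C(324, t). The two-sided p sums all outcomes no more probable than the one observed. The documents set no alpha for safety; 0.05 is assumed here.

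**Illustrations with assumed counts (PerClot versus control, different subjects in each row):**

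| Case | Overall incidence | Fisher p | Meets 5%? |
|---|---|---|---|
| Combined, 18 vs 6 | 24/324 = 7.4% | 0.018 | yes |
| Split evenly, 6 vs 2 in each of three rows | 8/324 = 2.5% | 0.28 each | no |
| Combined, 14 vs 3 | 17/324 = 5.2% | 0.011 | yes |
| Split, 5 vs 1, 5 vs 1, 4 vs 1 | at most 6/324 = 1.9% | 0.21, 0.21, 0.37 | no |
| Combined, 12 vs 0 | 12/324 = 3.7% | 0.0004 | no |
| Split, 4 vs 0 in each of three rows | 4/324 = 1.2% | 0.12 each | no |

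**Chance that the 5% threshold is met and p ≤ 0.05.** These are exact binomial calculations for assumed combined rates. For the split columns the figure is the chance that at least one row qualifies, with rows treated as independent:

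| Control vs PerClot | Combined | Split in halves | Split in thirds |
|---|---|---|---|
| 1% vs 3% | about 0 | about 0 | about 0 |
| 2% vs 6% | 8.5% | <0.1% | about 0 |
| 2% vs 8% | 34.6% | 0.5% | <0.1% |
| 3% vs 9% | 45.3% | 2.0% | <0.1% |
| 4% vs 12% | 69.9% | 16.2% | 1.1% |

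**What the composite would show in the first example.** The difference is 18/162 − 6/162 = 0.111 − 0.037 = 0.074. Its standard error is √(0.111 × 0.889/162 + 0.037 × 0.963/162) = 0.0288. The 95% Wald interval is 0.074 ± 1.96 × 0.0288, or about 1.8 to 13.1 percentage points.

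**Risk rating.** R81 has Medium probability and severity grade 5 before and after mitigation. That is chart value 10 in the sponsor's table, the highest residual value in the file, shared with R62, R86 and R90.

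**The case against.** The strongest reply is that the plan already has several safeguards.

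- **Recording.** Protocol 9.2 has each event entered once unless it recurs, and the form takes one short name. A reader might infer from the overlapping definitions that the same event will be counted twice. The data flow argues against that: the issue is which row an event lands in. A subject with two distinct events can still appear in two rows.
- **Visibility.** Every type is tabulated with an exact interval whatever its incidence, and events are also summarized by relatedness, seriousness and severity. The tests of serious device-related events and of unanticipated device effects pool across labels and have no 5% threshold. The DSMB reviews accumulating safety data (Protocol 9.4). It would be wrong to say that an excess goes unseen; it can go untested. Non-serious events, and serious events judged unrelated by an investigator who is not blinded, get no pooled comparison.
- **Status of the tests.** SAP 4.4.4 calls the safety analyses descriptive, with no formal hypotheses. That is so, but the same section plans Fisher tests, and a purely descriptive rate is also affected by ambiguous labels.
- **Device versus clot embolism.** The relatedness grade gives some separation, and the Glossary restricts thromboembolism to clots. It does not follow that the two cannot be told apart. But relatedness does not identify the embolic material, and R90 uses thromboembolism for product entering the vascular system, so usage is not consistent even within the protocol.
- **Case finding.** One thromboembolism checklist serves the postoperative and 6-week visits, and any positive answer leads to an adverse event form. Cases are thus sought together; the gap is in tabulation.
- **The threshold itself.** For rare events the 5% rule, more than the split, is the limit. Twelve versus 0 would go untested even if combined, and at 1% versus 3% neither arrangement is likely to be tested.

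**Conclusion.** The point stands as a reporting gap that is cheap to close. Following the plan as written gives rates for these types that depend on labelling, and it can leave a between-arm excess untested when the combined count would qualify. In the main illustration, a 7.4% combined incidence with p=0.018 becomes three rows at 2.5% with p=0.28.

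The size rests on assumptions: the documents give no embolic event rate, so the counts, the underlying rates, the even split and the 0.05 level are all chosen for illustration. What does not depend on them is that dividing related events among rows cannot raise any row's count above the combined count of those events.

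Two further inferences are not supported. Thrombosis, defined as local clotting, is not nested in embolism; only thromboembolism is. And R81 does not make this the single gravest risk: its rating is joint-highest, and the risk file does not always group the three terms, since R83 lists embolism and thrombosis without thromboembolism.

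**What to change.** In SAP 4.4.4 and Protocol 6.6.4, add one subject-level composite, any embolism, thromboembolism or thrombosis, reported by arm with the difference and its 95% confidence interval whatever its incidence. The last condition matters, because a composite subject to the 5% rule would still miss a case such as 12 versus 0.

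Below it, add exclusive sub-rows: thrombosis without embolus, embolus of clot, and embolus of device or other non-clot material. Assign them by a stated mapping from CTCAE short names and the event descriptions, done without knowledge of arm.

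The descriptions and short names are already collected, so no new data are needed, and the efficacy analysis and its alpha are untouched. The cost is SAP and protocol wording, one extra table, and a short blinded classification of what is likely to be a small number of events.
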